Amendment 1	01 December 2020	
This substantial amendment is making the following changes based on regulatory feedback from the US FDA and FAMHP.
 
• The PK stopping limit for AUC₂₄ are revised to be more conservative:
• 50% of exposure in male rats at NOAEL in 6 week toxicity study – ie, 18,400 ng•h/mL in Part 1 – refer to Table 1, Table 3, and Section 6.6.1;• 10% of exposure in male rats at NOAEL in 6 week toxicity study – ie, 3,680 ng•h/mL in Part 2 with revision to this stopping limit to be considered, via a protocol amendment post formal interim analysis, based on observed data in Part 1 and Part 2 in this study - refer to Number of Participants in Protocol Synopsis, Table 1, Table 4, Section 6.6.1, and Section 9.5.• Participants with abnormal eGFR, as well as newly added UACR, UPCR will be disqualified – refer to exclusion criterion 7 in Section 5.2, and Table 12.• Participants will be disqualified based on revised, more conservative limits for ALT and AST (in Part 1 and Part 3) and Total bilirubin (all 3 Parts) – refer to exclusion criterion 7 in Section 5.2.• CCI [REDACTED]• In Part 2, if the observed t_{1/2} of PF-07202954 is considerably longer than projected (in Part 1), provisions added that mandate consideration of Day 14

Document History		
Document	Version Date	Summary and Rationale for Changes
		
PK (along with Day 7) before initiation of dosing in the next cohort – refer to Section 6.6.1.
 
Added need for eye protection as part of caution for skin sensitivity to light and potential risk for sun burn – refer to Table 1 and Section 5.3.3.Cross reference to Table 1 added in Section 8.3.8 so as to acknowledge the potential risks based on completed nonclinical toxicity studies (with 1 or more of these potential risks classified as AESIs based on observed data from this study). 
In addition, the following administrative changes are also being incorporated:
 
Rationale for dosing with standard meal in Part 1 and Part 2 CCI [REDACTED] expanded in Section 4.2.5 and couple of references to substantiate this added.CCI [REDACTED]Definition of baseline, depending on endpoint has different predose nominal collection – note in Table 2 and Table 10 expanded to refer to SAP for definition of baseline for every single endpoint.CCI [REDACTED]Given potential for CYP3A induction, use of estrogen containing hormonal contraception and HRT was not permitted – this intent is clarified in Section 6.5.While female participants of CBP need to use highly

Document History		
Document	Version Date	Summary and Rationale for Changes
		effective method of contraception with low user dependency, in female partners of male participants use of both low user dependent and use dependent options were intended to be permitted given their lower risk – this intent clarified in Section 10.4.1 and Section 10.4.4.
Original protocol	02 October 2020	N/A

This amendment incorporates all revisions to date, including amendments made at the request of country health authorities and IRBs/ECs.

TABLE OF CONTENTS

LIST OF TABLES	10
LIST OF FIGURES	10
1. PROTOCOL SUMMARY	11
1.1. Synopsis	11
1.2. Schema	13
1.3. Schedule of Activities	14
2. INTRODUCTION	19
2.1. Study Rationale	19
2.2. Background	19
2.2.1. Nonclinical Pharmacology.....	20
2.2.2. Nonclinical PK and Metabolism.....	21
2.2.3. Biopharmaceutics	21
2.2.4. Nonclinical Safety	22
2.3. Benefit/Risk Assessment.....	22
2.3.1. Risk Assessment	23
2.3.2. Benefit Assessment.....	26
2.3.3. Overall Benefit/Risk Conclusion.....	26
3. OBJECTIVES AND ENDPOINTS	26
4. STUDY DESIGN.....	27
4.1. Overall Design.....	27
4.2. Scientific Rationale for Study Design	28
4.2.1. Study Population.....	28
4.2.2. Rationale for Part 1	28
4.2.3. Rationale for Part 2	30

1. PROTOCOL SUMMARY

1.1. Synopsis

Short Title: Multi-Part Study in Healthy Adults Evaluating Single- and Repeated-, Escalating, Oral Doses of PF-07202954 Plus Food Effect

Rationale: The current clinical study is the first one proposed with PF-07202954. It is designed as a 3-part study in healthy adults. Part 1 will evaluate the safety, tolerability, and plasma PK CCI [REDACTED] with administration of escalating, single, oral doses of PF-07202954 with a standard morning meal. Part 2 will evaluate safety, tolerability, and plasma and urine PK CCI [REDACTED] with repeated, escalating doses of PF-07202954 administered once daily with a standard morning meal for 14 days. Based on observed data from Part 1 and Part 2, Part 3 may be conducted to assess the effect of a high-fat/high-caloric meal versus a fasted state on the plasma PK of PF-07202954.

Objectives and Endpoints: The key objectives and endpoints for Part 1, Part 2, and Part 3 (if conducted) of this study are summarized below –

Study	Objectives	Endpoints
Part 1		
Primary	To evaluate safety and tolerability of single , oral, escalating doses of PF-07202954 administered with a standard morning meal in healthy, adult participants.	Following assessments over ≥ 10 days of each Period and up to Day 30 ± 2 days post last dose of study intervention – 
• AEs;• Clinical laboratory tests;• Vital signs (including BP and pulse rate);• Cardiac conduction intervals via 12-lead ECG.
Secondary	To characterize the plasma PK profile of PF-07202954 following administration of single , oral, escalating doses.	PK parameters ^a derived from plasma PF-07202954 concentrations: 
• C_{max}, T_{max}, AUC_{last}, AUC_{inf}, $t_{1/2}$, as data permit.
Part 2		
Primary	To evaluate safety and tolerability of repeated , oral, escalating doses of PF-07202954 administered with a standard morning meal in healthy, adult participants with simple hepatic steatosis.	Following assessments over the duration of dosing and up to Day 30 ± 2 days post last dose of study intervention – 
• AEs;• Clinical laboratory tests;• Vital signs (including BP and pulse rate);• Cardiac conduction intervals via 12-lead ECG.
Secondary	To characterize the plasma and urine PK profiles of PF-07202954 following administration of repeated , oral, escalating doses.	PK parameters ^a derived from plasma PF-07202954 concentrations: 
• Single dose: C_{max}, T_{max}, AUC_{tau} on Day 1;• Repeated dose:
• Days 7 and 14 – C_{max}, T_{max}, AUC_{tau}, as data permit;• Day 14 – $t_{1/2}$ as data permit. PK parameters ^a derived from urine PF-07202954 concentrations on Day 14 : Ae_{tau} , $Ae_{tau}\%$, CL_T .

Study	Objectives	Endpoints
Part 3, if conducted		
Primary	To characterize the effect of a high-fat/high-caloric meal , compared to following an overnight fast, on plasma PK profile of PF-07202954 following administration of a single oral dose to healthy, adults.	PK parameters ^a derived from plasma PF-07202954 concentration: 
• C_{max}, T_{max}, AUC_{last}, and AUC_{inf}, as data permit.
Secondary	To evaluate safety and tolerability of a single , oral, dose of PF-07202954 administered with a high-fat/high-caloric meal compared to following an overnight fast.	Following assessments over ≥ 5 days of each Period and up to Day 30 ± 2 days post last dose of study intervention – 
• AEs;• Clinical laboratory tests;• Vital signs (including BP and pulse rate);• Cardiac conduction intervals via 12-lead ECG.

a. For a complete definition of all PK parameters refer to [Table 8](#) and [Table 9](#).

NOTE: For all non-PK related endpoints, **baseline is defined** as the time-matched data obtained while on placebo [Part 1], 0H assessment on Day 1 or 0-12H or 0-24H assessment prior to 1st dose [Part 2], **or** 0H assessment on Day 1 in **each** Period [Part 3], unless otherwise specified in the SAP.

Overall Design: The study is planned as a 3-part design with investigator- and participant- blinded (sponsor-open), placebo-controlled, randomized, dose-escalation in Part 1 and Part 2; and a randomized, open-label design, in Part 3 (if conducted).

Number of Participants: In this study, participants can be randomized and receive the study intervention in 1 of the 3 parts, **only**. However, participants may be screened for more than 1 part of the study.

Part 1 ^a	16 participants (8 per cohort) 
• 6 active +2 placebo per dose level
Part 2 ^a	Initially 30-40 participants with 10 participants per cohort (with potential to expand to 50 [minimum] to 60 [maximum] post formal IA and protocol amendment) 
• 8 active +2 placebo per cohort
Part 3, ^a if conducted	8 (minimum) to 12 (maximum) participants 
• Sample size guided by observed variability in plasma PK in Part 1

a. Participants prematurely withdrawn may be replaced at investigator discretion *in consultation* with the sponsor

A total of up to 88 unique participants are planned to be randomized in this study.

Note: "Enrolled" means a participant's agreement to participate in a clinical study following completion of the informed consent process **and randomization**. Potential participants who are screened for the purpose of determining eligibility for the study, but do **not** participate in the study, are **not** considered "enrolled".

Intervention Groups and Duration: In this study, the study interventions include PF-07202954 and placebo – both as extemporaneously prepared suspensions for oral administration. In Part 1 and Part 3, participants will receive single doses. In Part 2, participants will receive study intervention once daily for 14 days.

DMC or Other Independent Oversight Committee: No

Statistical Methods: The sample size for Part 1 (single, escalating doses) and Part 2 (repeated, escalating doses) has been chosen based on the need to minimize first exposure to humans of a new chemical entity and the requirement to provide adequate safety and toleration information at each dose level. For Part 3, a range of assumed variability estimates for plasma PK were used to derive the sample size that permits a sufficiently precise assessment with probable 90% CI for an effect size of 1.0 (ie, no change in exposure with and without food).

The data from the three Parts of this study will be analyzed separately and reported in a single CSR. All safety analyses will be performed on the Safety Analysis Set defined as all participants randomly assigned to study intervention and who consume at least 1 dose of study intervention. Safety data will be presented in tabular and/or graphical format and summarized descriptively, where appropriate.

The PK parameters for PF-07202954 following oral dose administration will be derived from the concentration-time profiles. PK parameters and concentrations of PF-07202954 will be descriptively summarized by dose and time, as appropriate.

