This part will be a single cohort, randomized, open-label, 2-period, crossover design, randomizing 8 (minimum) to 12 (maximum) participants who will receive PF-07202954 once with a high-fat/high-caloric meal and once following an overnight fast of ≥ 10 hours with the order randomly assigned. Since the dose in this part (refer to [Section 4.3.5](#)) will be selected based on observed safety, tolerability, and PK of single doses in Part 1 and the dose selected will be lower than the highest dose tested in Part 1, standard safety monitoring will be used in this part of the study.

4.2.5. Rationale for Dosing with Standard Meal in Part 1 and Part 2

In Part 1 and Part 2 of this study, PF-07202954 will be administered with a standard morning meal because PF-07202954 is expected to be administered with food in clinical practice and administration with a meal helps in the assessment of the effect of PF-07202954 [REDACTED]

[REDACTED] Although food is expected to have minimal impact on PF-07202954 exposures at doses ≤ 1500 mg based on the physical and chemical properties of PF-07202954 and simulations of a PBPK model, the effect of a high-fat/high-caloric meal on plasma concentrations of PF-07202954 may be evaluated in Part 1 and/or Part 3 of this study.

CC1 [REDACTED]

[REDACTED]

[REDACTED]

[REDACTED]

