9.4.3.2. Statistical Methods for PK Data

No formal inferential statistics will be applied to the plasma PK data from Part 1 and 2. In Part 3, if conducted, the statistical comparison of plasma PK under high-fat/high-caloric state (test) versus fasted (reference) condition is envisioned.

- **Part 1 (Single, Escalating Doses):** Plasma concentrations of PF-07202954 will be descriptively summarized and plotted by nominal PK sampling time and dose:

- The plasma PK parameters AUC_{inf} , C_{max} , AUC_{last} , T_{max} , T_{lag} , CL/F , V_z/F , and $t_{1/2}$ will be summarized descriptively by dose;

[REDACTED]

[REDACTED]

- **Part 2 (Repeated, Escalating Doses):** Plasma concentrations of PF-07202954 will be descriptively summarized and plotted by nominal PK sampling time, day, and dose:

- The plasma PK parameters AUC_{tau} , C_{max} , T_{max} , T_{lag} , $t_{1/2}$, C_{min} , C_{av} , PTR , CL/F , V_z/F , $R_{ac,AUC_{tau}}$, and $R_{ac,Cmax}$, and the urine PK parameters Ae_{tau} , $Ae_{tau}\%$, and CL_r will be summarized descriptively by dose and day as applicable;

[REDACTED]

- Median morning trough (predose) plasma concentrations will be plotted by day (all doses on the same plot) in order to assess the attainment of steady state.

- **Part 3 (Single-Dose Food Effect, if conducted):** To compare PF-07202954 exposures following high-fat/high-caloric meal (Test) versus following an overnight fast (Reference) natural log-transformed C_{max} , AUC_{last} , and AUC_{inf} (if data permit) will be analyzed using a mixed effects model with treatment as a fixed effect and participant as a random effect. Period may also be included as a factor in the model. Estimates of the adjusted mean differences (Test-Reference) and corresponding 90% CIs will be obtained from the model. The adjusted mean differences and 90% CIs for the differences will be exponentiated to provide estimates of the ratio of adjusted geometric means (Test/Reference) and 90% CIs for the ratios.

- ***In addition –***

- Plasma concentrations of PF-07202954 will be descriptively summarized and plotted by nominal PK sampling time and treatment;
- The plasma PK parameters AUC_{inf} , C_{max} , AUC_{last} , T_{max} , T_{lag} , CL/F , V_z/F , and $t_{1/2}$ will be summarized descriptively by treatment;
- For AUC_{inf} , C_{max} , and AUC_{last} , box and whisker plots will be presented by treatment and overlaid with geometric means.

CCI

CCI

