### 6.1. Primary Endpoint(s)

The primary endpoints in Part 1 and Part 2 are related to safety/tolerability whose analyses are described Section 6.6.

The primary endpoints in Part 3 are the plasma PK endpoints whose analyses are described in Section 6.2.

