**TABLE 7. PLASMA PK PARAMETERS TO BE SUMMARIZED DESCRIPTIVELY**

Parameter	Summary Statistics
AUC inf , AUC last , C max , AUC inf(dn) , AUC last(dn) , AUC tau , AUC tau(dn) , C max(dn) , CL/F, V z /F, C min , PTR, AUC tau , C av , R ac,AUCtau , and R ac,Cmax	N, arithmetic mean, median, %CV, standard deviation (SD), minimum (min), maximum (max), geometric mean and geometric %CV
T max , T lag	N, median, min, max.
t 1/2	N, arithmetic mean, median, %CV, SD, min, max.

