**TABLE 8. URINE PK PARAMETERS TO BE SUMMARIZED DESCRIPTIVELY**

Parameter	Summary Statistics
Ae tau , Ae tau % and CL r	N, arithmetic mean, median, %CV, SD, min, max, geometric mean and geometric %CV.

- **Part 1 (Single, Escalating Doses):**
- Plasma concentrations of PF-07202954 will be descriptively summarized and plotted by nominal PK sampling time and dose.

- The plasma PK parameters  $AUC_{inf}$ ,  $C_{max}$ ,  $AUC_{last}$ ,  $T_{max}$ ,  $T_{lag}$ ,  $CL/F$ ,  $V_z/F$ , and  $t_{1/2}$  will be summarized descriptively by dose;

[REDACTED]

[REDACTED]

- **Part 2 (Repeated, Escalating Doses):**

- Plasma concentrations of PF-07202954 will be descriptively summarized and plotted by nominal PK sampling time, day, and dose;
- The plasma PK parameters  $AUC_{tau}$ ,  $C_{max}$ ,  $T_{max}$ ,  $T_{lag}$ ,  $t_{1/2}$ ,  $C_{min}$ ,  $C_{av}$ ,  $PTR$ ,  $CL/F$ ,  $V_z/F$ ,  $R_{ac,AUC_{tau}}$ , and  $R_{ac,Cmax}$ , and the urine PK parameters  $Ae_{tau}$ ,  $Ae_{tau}\%$ , and  $CL_r$  will be summarized descriptively by dose and day as applicable;

[figure not shown]
[figure not shown]
[REDACTED]

- Median morning trough (predose) plasma concentrations will be plotted by day (all doses on the same plot) in order to assess the attainment of steady state.
- **Part 3 (Single-Dose Food Effect, if conducted):** To compare PF-07202954 exposures following high-fat/high-caloric meal (Test) versus following an overnight fast (Reference) natural log-transformed  $C_{max}$ ,  $AUC_{last}$ , and  $AUC_{inf}$  (if data permit) will be analyzed using a mixed effects ANOVA described in Section 5.2. Estimates of the adjusted mean differences (Test-Reference) and the corresponding 90% CIs will be obtained from the model. The adjusted mean differences and 90% CIs for the differences will be exponentiated to provide estimates of the ratio of adjusted geometric means (Test/Reference) and 90% CIs for the ratios.

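### Tmax is a Part 3 primary food-effect endpoint, but no within-participant fed-versus-fasted difference or interval is planned for it (minor, cheap to fix)

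*Protocol*

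**What the plan says.** The protocol synopsis, protocol Table 2 and SAP Table 2 set a comparative primary objective for Part 3. The high-fat/high-caloric breakfast is the test condition, and the objective puts the contrast in these terms: "compared to following an overnight fast, on plasma PK profile of PF-07202954 following administration of a single oral dose to healthy, adults". The endpoints on that line are "C_{max}, T_{max}, AUC_{last}, and AUC_{inf}, as data permit". The design is paired. Protocol Section 4.2.4 states: "This part will be a single cohort, randomized, open-label, 2-period, crossover design", with each participant dosed once fed and once fasted.

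SAP Section 6.1 points to one place for the analysis: "The primary endpoints in Part 3 are the plasma PK endpoints whose analyses are described in Section 6.2". There, log-transformed Cmax, AUClast and AUCinf "will be analyzed using a mixed effects ANOVA described in Section 5.2", giving Test/Reference ratios with 90% CIs. Protocol Section 9.4.3.2 names the same three parameters, which "will be analyzed using a mixed effects model with treatment as a fixed effect and participant as a random effect".

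Tmax appears only in the list of parameters summarised descriptively by treatment. SAP Table 7 limits that summary to "N, median, min, max". The Part 3 box plots also leave Tmax out.

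**The concern.** Three of the four primary endpoints get an estimate of the food effect with an interval. The fourth gets two separate summaries that the reader must compare by eye. Each of the 8 to 12 participants supplies both a fed and a fasted Tmax, so a per-participant difference is available at no cost, but the planned output does not use it.

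What is at stake is modest but real. Two medians and two ranges do not show whether a delay is consistent across people, and they carry no statement of uncertainty about the shift.

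**Working it through.** **1. Planned output by endpoint (protocol 9.4.3.2, SAP 6.2, SAP Table 7)**

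| Part 3 primary endpoint | Fed/fasted model | Ratio and 90% CI | Summary by meal state | Box plot |
|---|---|---|---|---|
| Cmax | yes | yes | yes | yes |
| AUClast | yes | yes | yes | yes |
| AUCinf (as data permit) | yes | yes | yes | yes |
| Tmax | no | no | N, median, min, max | no |

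**2. Could other text supply the contrast?** SAP Section 5.2 allows non-parametric analyses if the ANOVA assumptions fail. That option is conditional and is not assigned to Tmax. The interval for a median difference described there is an 80% CI against the placebo group; Part 3 has no placebo and no pairing is described. Parts of the SAP are redacted, but the Part 3 lists in protocol 9.4.3.2 and SAP 6.2 are readable and agree.

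**3. The plan's own precision figures.** Protocol Table 6 reproduces with log half-width

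h = t(0.95, n−2) × SD × √(2/n) × √(χ²(0.80, n−2)/(n−2)).

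For n = 12 and SD = 0.24: 1.812 × 0.24 × 0.408 × √(13.44/10) = 0.206. Then exp(±0.206) gives 0.814 to 1.229, against 0.81 to 1.23 in the table. All nine cells match within rounding. These figures concern log-transformed exposure (the text names AUCinf). The documents hold nothing equivalent for Tmax, and give no Tmax SD.

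**4. Same table, different pairing (invented values, n = 8).** Fasted Tmax: 1, 1, 2, 2, 2, 3, 3, 4 h. Fed Tmax: 2, 2, 3, 3, 3, 4, 4, 5 h. The planned summary is median 2 (range 1 to 4) versus median 3 (range 2 to 5), however the values are paired.

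- Paired in the order shown, every difference is +1 h. The Hodges-Lehmann estimate is +1.0 h, interval 1.0 to 1.0.
- With the fed values reversed, the differences are 4, 3, 2, 1, 1, 0, −1, −2 h. The estimate is again +1.0 h, but the interval is −0.5 to 2.5.

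The interval limits are the 6th smallest and 6th largest of the 8 × 9/2 = 36 pairwise averages.

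**5. Is an interval feasible at this sample size?** For n = 8, the rank subsets with sum 5 or less number 1+1+1+2+2+3 = 10 out of 2⁸ = 256. Coverage of the nominal 90% signed-rank interval is therefore 1 − 2 × 10/256 = 92.2%. The same count gives 91.6% for n = 10 and 90.8% for n = 12. These values assume no ties and symmetric differences.

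**6. Illustrative precision.** Only n (8 and 12) and the sampling times (0.5 to 24 h, SoA Table D) come from the documents. Assumed: log-normal Tmax; fasted median 3 or 5 h; between-participant log SD 0.3 or 0.4; within-participant log SD 0.2 or 0.3; fed/fasted factor 1.0, 1.3 or 1.6; values moved to the nearest sampling time; 20,000 simulated trials per setting.

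- The SE of the difference of separate medians was about 0.44 to 1.7 h. The paired Hodges-Lehmann SE was about 0.29 to 1.3 h. The ratio was 0.54 to 0.88, median 0.74.
- A Hodges-Lehmann shift that ignores pairing separates the sources of the gain. The paired SE had a median ratio of 0.96 to this unpaired SE, and exceeded it in some settings.

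| Setting (n, fasted median, between/within log SD, factor) | Separate medians | Unpaired HL | Paired HL |
|---|---|---|---|
| 8, 3 h, 0.3/0.2, 1.0 | 0.51 h | 0.37 h | 0.35 h |
| 12, 5 h, 0.4/0.2, 1.0 | 0.79 h | 0.29 h | 0.46 h |
| 12, 5 h, 0.3/0.2, 1.3 | 1.25 h | 1.02 h | 0.67 h |

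In the first row, 0.14 of the 0.16 h reduction comes from changing the estimator and only 0.02 h from pairing. In the second row pairing makes the SE larger. In the third it helps clearly.

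**The case against.** The best defence is that this is a reporting choice in an estimation-only study. The objective is to characterise the effect. Protocol Section 9.1 plans no hypothesis tests, and the SAP has no decision rules (Section 5.1) and no estimands (Section 2.1). Sample size rests on AUCinf, and Part 3 is optional. No dose choice or bound depends on Tmax, and Table 7 treats it the same way in every Part. All of this stands and keeps the point minor. It does not remove it, because the same estimation-only plan gives the other three primary endpoints an effect estimate and an interval.

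A reader might infer more than the documents support:

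- *That Part 3 cannot show a food effect on Tmax.* It can. The fed and fasted medians sit side by side and concentrations are plotted by treatment, so a shift is visible. The paired estimate and its interval are what is absent.
- *That the pairing is lost.* It is only unused in the planned summary; the individual values remain in the data.
- *That protocol and SAP contradict each other.* On which parameters are modelled, they agree.
- *That pairing brings the whole precision gain.* The last table above shows that it does not.

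The remedy also has limits. Tmax falls on a coarse grid (3, 4, 5, 8, 12 h), so ties will be heavy. The signed-rank interval assumes symmetric differences, which a multiplicative food effect would not give.

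**Conclusion.** The gap is confirmed from the text: Tmax is a primary endpoint under a fed-versus-fasted objective, and no within-participant difference or interval is planned for it. The example in step 4 supports the main consequence without any variance assumption: the planned table is identical for a uniform and an inconsistent shift.

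The gain in precision cannot be derived from the documents. Under the assumed log SDs it is roughly 10-45% in SE relative to the difference of separate medians, and much of that comes from the estimator and the sampling grid. It should not be quoted as the benefit of pairing. This is a minor improvement, not a flaw that threatens Part 3.

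**What to change.** In SAP Section 6.2 (Part 3) and protocol Section 9.4.3.2, add for Tmax the within-participant fed-minus-fasted difference, using actual sampling times. Report the Hodges-Lehmann median difference with a distribution-free 90% CI, the level already used for the other three endpoints. State that coverage is approximate because of ties on the sampling grid and the symmetry assumption. If adjustment for period is wanted, the two-sequence form of the same estimator can be used. Keep the median and range by meal state. If the sponsor means Tmax to be purely descriptive, the endpoint tables should say so.

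The cost is one sentence and one table line, with no new data and no change in conduct. Both documents reserve a protocol amendment for major modifications of a primary endpoint's definition or analysis. The sponsor should record whether this addition counts as one, or make it at the next amendment.
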